### Wound Healing and Surgery

VEGF inhibitors can cause wound healing complications and wound dehiscence which may occur even long after a wound has been considered healed. Therefore, surgical and traumatic wounds must have completely healed prior to starting study treatment and be monitored for wound dehiscence or wound infection while the subject is being treated with study drug.

Study treatment should be stopped at least 28 days prior to scheduled surgery. The decision to resume study treatment after surgery should be based on clinical judgment of adequate wound healing. Study treatment should be interrupted for any wound healing complication. Study treatment should be discontinued in subjects with serious or chronic wound healing complications.

### **6.7.7 Hypertension**

Hypertension is a common class effect of drugs that inhibit VEGF pathways and has been reported in subjects treated with cabozantinib.

Blood pressure should be monitored in a constant position at each visit (either sitting or supine). Treatment guidelines for hypertension deemed related to blinded study drug are presented in Table 6-6. In general, subjects with known hypertension should be optimally managed prior to study entry. Decisions to decrease or hold the dose of study treatment must be based on BP readings taken by a medical professional and must be confirmed with a second measurement at least 5 minutes following the first measurement. Other than for hypertension requiring immediate therapy, the presence of new or worsened hypertension should be confirmed at a second visit before taking therapeutic action. It is recommended that this second visit occurs within 1 week.

**Table 6-6: Guidelines for the Management of Treatment-emergent Hypertension**

Criteria for Dose Modification a	Blinded Study Dose Modification
Subjects NOT receiving optimized antihypertensive therapy	
> 150 mm Hg (systolic) and < 160 mm Hg OR > 100 mm Hg (diastolic) and < 110 mm Hg	
 
Optimize antihypertensive treatment by adding new or additional antihypertensive medications and/or increase dose of existing medications.
 
Reduce study treatment by one dose level if optimal antihypertensive therapy (usually to include 3 agents) does not result in BP < 150 mm Hg systolic or < 100 mm Hg diastolic,
 
If subject is symptomatic interrupt study treatment
 

≥ 160 mm Hg (systolic) OR ≥ 110 mm Hg (diastolic)	
 
Reduce study treatment by 1 dose level
 
Add new or additional antihypertensive medications and/or increase dose of existing medications and monitor subject closely for hypotension. If optimized antihypertensive therapy (usually to include 3 agents) does not result in BP < 150 mm Hg systolic or < 100 mm Hg diastolic, study treatment should be dose reduced further or interrupted
 
Study treatment should be dose interrupted if upper limits of BP (≥ 160 mm Hg systolic or ≥ 110 mm Hg diastolic) are sustained and not adequately manageable or if BP is > 180 mm Hg systolic or > 120 mm Hg diastolic or if subject is symptomatic.
 
Restart study treatment at the most tolerable dose and reescalate only if BP falls to and is sustained at < 140 mm Hg systolic and < 90 mm Hg diastolic.
 

Hypertensive emergency b or hypertensive encephalopathy	
 
Discontinue study treatment
 

a The investigator may decide to initiate or adjust antihypertensive treatment at a lower threshold than systolic BP > 150 mm Hg or diastolic BP > 100 mm Hg based on their clinical judgment and assessment of the individual subject.

b Hypertensive emergency is defined as uncontrolled elevated blood pressure with clinical evidence of progressive or impending end-organ damage (ie, myocardial infarction/ischemia, intracranial hemorrhage, cerebral ischemia, pulmonary edema, encephalopathy, kidney damage)

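### Protocol Table 6-6: the blood-pressure target after optimized therapy joins its two limits with *or*, so read literally a subject left at 155/85 or 145/105 is at target and the table calls for no dose step

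*Protocol*

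**What the plan says.** Table 6-6 gives its two blood-pressure rows under the header "Subjects NOT receiving optimized antihypertensive therapy". The first row is entered at "> 150 mm Hg (systolic) and < 160 mm Hg OR > 100 mm Hg (diastolic) and < 110 mm Hg". The second is entered at 160 or above systolic or 110 or above diastolic. In both rows, one raised component is enough for entry.

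In the first row, antihypertensive treatment is optimized, and then: "Reduce study treatment by one dose level if optimal antihypertensive therapy (usually to include 3 agents) does not result in BP" below 150 systolic or below 100 diastolic. A symptomatic subject is interrupted. In the second row the dose is reduced by one level on entry. If optimized therapy then "does not result in BP < 150 mm Hg systolic or < 100 mm Hg diastolic", "study treatment should be dose reduced further or interrupted". That row also interrupts treatment for sustained, unmanageable pressure at 160 or 110 and above, for pressure above 180 or 120, or for symptoms.

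Three other places use the same or related limits:

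- The re-escalation line in Table 6-6 requires that pressure falls to and "is sustained at < 140 mm Hg systolic and < 90 mm Hg diastolic".
- Footnote a to the table lets the investigator start or adjust antihypertensives "at a lower threshold than systolic BP > 150 mm Hg or diastolic BP > 100 mm Hg".
- Exclusion criterion 8.a.ii (Section 4.3, repeated for crossover in Appendix B) treats sustained pressure above 150 systolic, or above 100 diastolic, on optimal treatment as uncontrolled.

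**The concern.** The rows open when either component is too high, so the target that closes them should require both components to be controlled. The wording instead puts *or* between the two limits after a negative. One ordinary reading of *does not achieve A or B* is *achieves neither*. On that reading a subject whose systolic pressure stays at 155 is at target because the diastolic is 85, although the pressure that opened the row has not changed.

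What is at stake is a dose step in asymptomatic subjects with persistent hypertension on study drug. Section 6.7.7 ties the step to measured values: "Decisions to decrease or hold the dose of study treatment must be based on BP readings taken by a medical professional". The exact thresholds and the word joining them are therefore what sites would apply. The table will be used: Section 1.3.3.1 reports hypertension in 29% of 2410 pooled single-agent subjects, at Grade 3 or higher in 14%. Those rates do not show how many subjects would fall in the gap.

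**Working it through.** There is no planned figure to reproduce. The check is one of logic, using the limits in Table 6-6 and criterion 8.a.ii. Let S be systolic and D diastolic pressure in mm Hg after optimization.

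1. Row 1 entry, leaving out values that reach row 2: S > 150 or D > 100. Criterion 8.a.ii uses the same limits.
2. Literal reading of the target: act if not (S < 150 or D < 100), which equals S ≥ 150 **and** D ≥ 100.
3. *And* with the present signs: act if not (S < 150 and D < 100), which equals S ≥ 150 **or** D ≥ 100.
4. *And* with ≤: act if not (S ≤ 150 and D ≤ 100), which equals S > 150 **or** D > 100. This is identical to step 1.

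| Reading | Above 150 or above 100 | Literal *or*: act? | < 150 and < 100: act? | ≤ 150 and ≤ 100: act? |
|---|---|---|---|---|
| 155/85 | yes | **no** | yes | yes |
| 145/105 | yes | **no** | yes | yes |
| 155/105 | yes | yes | yes | yes |
| 145/95 | no | no | no | no |
| 150/100 | no | yes | yes | no |
| 150/85 | no | no | yes | no |
| 145/100 | no | no | yes | no |

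The readings were chosen to show the logic; their counts say nothing about frequency.

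In whole mm Hg, the pattern missed on the literal reading is S from 151 to 159 with D below 100, or D from 101 to 109 with S below 150, persisting without symptoms on optimized therapy. These values lie below the 160 or 110 limits in row 2, so its interruption rule does not catch them.

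The consequence differs by row. A first-row subject has had no earlier reduction under the table and on the literal reading gets none: 60 mg stays 60 mg where the intended reading gives 40 mg (Table 6-4). A second-row subject was reduced on entry, so only the further reduction or interruption is lost.

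The other text points to the either-limit meaning. Entry to both rows, footnote a and criterion 8.a.ii each respond to one component alone, and the re-escalation line uses *and* where both limits must hold. Under Appendix B, a placebo subject with sustained 155/85 on optimal therapy could not cross over to cabozantinib; on the literal reading of Table 6-6, a first-row subject already taking it at that pressure need not be reduced.

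**The case against.** The strongest reply is that the literal reading defeats itself. A subject who enters row 1 at 155/85 would be at target before any drug was added, so the step could not operate unless the diastolic also rose. A site would be unlikely to adopt a reading that empties the row. The elliptical reading (fails on systolic, or fails on diastolic) works, and the surrounding text supports it. This stands as evidence of intent and is why most clinicians would probably get it right. It does not make the sentence say so.

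A reader might also infer that the protocol leaves such a subject with no dose provision anywhere. The documents do not support that. Section 6.5.1 says reductions or interruptions should be considered when supportive care is ineffective, and it permits modification at lower grades for safety. Table 6-3 has general rules for Grade 3 events and for intolerable Grade 2 events that cannot be managed. Its note points to Section 6.7 for specific conditions without saying that the general rows cease to apply. Whether 145/105 would fall under them depends on CTCAE hypertension grades that the documents do not give. Section 5.2 has the treating physician confirm suitability to continue at each visit. The gap is therefore in Table 6-6 itself.

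Finally, the table is titled as guidelines, so calling its steps mandatory would be too strong. That is accepted. A guideline that gives numeric limits should still give them without ambiguity.

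**Conclusion.** The point holds as a minor subject-safety wording correction. Read literally, both target lines of Table 6-6 treat control of one component as success, contrary to the entry criteria of the same rows, to criterion 8.a.ii and to the re-escalation line. The size is one dose step per affected subject, for asymptomatic subjects within the range shown above. How many subjects that would be, and how many sites would read the line literally, cannot be estimated from the documents.

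Two further inferences should be resisted. The wording does not show that the sponsor meant to tolerate a single raised component; the other text points the other way. Nor does it touch the OS, PFS or ORR analyses, the alpha allocation or the power. The conclusion rests on the text of the two lines and on the surrounding criteria as evidence of intent.

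**What to change.** In both target lines of Table 6-6, make the dose step follow when optimized therapy does not bring blood pressure to ≤ 150 mm Hg systolic **and** ≤ 100 mm Hg diastolic, and add in parentheses that both limits must be met. This matches criterion 8.a.ii and the row 1 entry threshold exactly. Keeping the present signs with *and* (< 150 and < 100) is an acceptable, slightly more cautious alternative; it also triggers the step at exactly 150 or exactly 100, which 8.a.ii does not call uncontrolled.

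Leave the entry criteria, the interruption rule at 160 or 110, and the re-escalation line as they are. The cost is one conjunction, two inequality signs and a short parenthesis in each of two lines, made in the next amendment or in a clarification letter to sites. Data collection and analysis do not change.

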### 6.7.8 Thromboembolic Events

Thromboembolic complications are frequent in cancer patients due to procoagulant changes induced by the malignancy or anticancer therapy including inhibitors of VEGF pathways. DVT and PE have been observed in clinical studies with cabozantinib; including fatal events (please refer to the Investigator’s Brochure). Subjects who develop a PE or DVT should have study treatment held until therapeutic anticoagulation with heparins (LMWH) is established. (Note: therapeutic anticoagulation with oral anticoagulants is prohibited.)

Study treatment may be resumed in subjects with PE or DVT if it is determined that the event is uncomplicated, they are deriving benefit from study treatment, and that anticoagulation does not place them at a significant risk that outweighs the benefit of resuming treatment. During treatment with anticoagulants, subjects need to be monitored on an ongoing basis for bleeding risk and signs of bleeding. Subjects with life-threatening PE or DVT should have study treatment discontinued unless toxicity can be managed and subject is deriving clear clinical benefit as determined by the investigator and agreed by the Sponsor.

Subjects who develop portal/hepatic vessel thrombosis may not require anticoagulation. The decision regarding anti-coagulation in such cases is at the discretion of the investigator and within the context of standard of care.

Arterial thrombotic events (eg, transient ischemic attack, myocardial infarction) have been observed rarely in studies with cabozantinib. Subjects should be evaluated for preexisting risk factors for arterial thrombotic events such as diabetes mellitus, hyperlipidemia, hypertension, coronary artery disease, history of tobacco use, and cardiac or thromboembolic events that occurred prior to initiation of study treatment. Study treatment should be discontinued in subjects who develop an acute myocardial infarction or any other clinically significant arterial thromboembolic complication.

#### **6.7.9 Proteinuria**

Proteinuria is an anticipated AE with the inhibition of VEGF pathways and has been observed in cabozantinib clinical studies, and nephrotic syndrome has been reported with cabozantinib and other inhibitors of VEGF pathways.

During each safety assessment visit, proteinuria will be quantified by measuring the urine protein-to-creatinine (UPCR) ratio performed by the central lab. In addition, urine dipstick analysis performed by the local lab will be done at least every 8 weeks and more as clinically indicated. Management of proteinuria will be based on UPCR results provided by the central lab (see Table 6-7).

As dipstick results from the local labs may be available prior to the UPCR results from the central lab, they can be used by the investigator for interim management. In the case of proteinuria, if the dipstick analysis shows proteinuria  $\geq 3+$ , study treatment should be interrupted until the UPCR results are available and more definitive management can be applied.

**Table 6-7: Management of Treatment-emergent Proteinuria**

Severity of Proteinuria (UPCR)	Action To Be Taken
≤ 1 mg/mg (≤ 113.1 mg/mmol)	
 
No change in study treatment or monitoring
 

> 1 and < 3.5 mg/mg (> 113.1 and <395.9 mg/mmol)	
 
No change in study treatment required
 
Consider confirming with a 24-hour protein excretion within 7 days
 
Repeat UPCR within 7 days and once per week. If UPCR < 1 on 2 consecutive readings, UPCR monitoring can revert to protocol-specific times. (Second reading is confirmatory and can be done within 1 week of first reading.)
 

≥ 3.5 mg/mg (≥ 395.9 mg/mmol)	
 
Hold study treatment pending repeat UPCR within 7 days and/or 24-hour urine protein.
 
If ≥ 3.5 on repeat UPCR, continue to hold study treatment and check UPCR every 7 days. If UPCR decreases to < 2, restart study treatment at a reduced dose and monitoring of urine protein/creatinine should continue weekly until the UPCR decreases to < 1.
 

Nephrotic syndrome	
 
Discontinue study treatment
 

UPCR = Urine Protein Creatinine Ratio

### 6.7.10 Corrected QTc Prolongation

The effect of orally administered cabozantinib at 140 mg/day (FBE) on QTc interval was evaluated in a randomized, double-blinded, placebo-controlled Phase 3 study in patients with MTC (Study XL184-301). A mean increase in QT interval corrected by Fridericia (QTcF) of 10-15 ms was observed at 4 weeks after initiating cabozantinib. A concentration-QTc relationship could not be definitively established. Changes in cardiac wave form morphology or new rhythms were not observed. No cabozantinib treated patients on this study had a QTcF > 500 ms during the QT evaluation period.

Only subjects with a baseline QTcF ≤ 500 ms are eligible for this study. Subjects will have ECGs performed at times designated by the protocol (Section 5.2).

If at any time on study there is an increase in QTcF interval to an absolute value > 500 ms, within 30 minutes after the initial ECG, 2 additional ECGs must be performed each with intervals approximately 3 minutes apart.

If the average QTcF from the 3 ECGs is  $> 500$  ms, the following actions must be taken:

- Withhold study treatment
- Immediately notify the Sponsor
- Hospitalize symptomatic subjects (eg, with palpitations, dizziness, syncope, orthostatic hypotension, a significant ventricular arrhythmia on ECG) for a thorough cardiology evaluation and management
- Consider cardiology consultation for asymptomatic subjects for evaluation and management
- Check electrolytes, especially magnesium and potassium; correct abnormalities as clinically indicated
- Check concomitant medications for any medication that may have contributed to QT prolongation, and if possible, discontinue these medications (see <http://www.qtdrugs.org>)
- Send ECGs to central ECG laboratory (see ECG study manual)
- Repeat ECG triplicates hourly until the average QTcF is  $\leq 500$  ms

Study treatment may be restarted at a reduced dose level if all of the following conditions are met:

- Symptoms are determined to be unrelated to the QT interval prolongation
- The QTcF value  $> 500$  ms is not confirmed by the central ECG laboratory or a QTcF  $> 500$  ms confirmed by the central laboratory returns to  $\leq 500$  ms
- Study treatment has been interrupted through a minimum of 1 week following the return of the QTcF to  $\leq 500$  ms
- Sponsor has reviewed all available information and has agreed to the continuation of study treatment

Following reinitiation of study treatment, ECGs must be repeated weekly for 2 weeks, then every 2 weeks for 1 month, then according to the protocol-defined time points.

Study treatment must be permanently discontinued if either of the following applies:

- Cardiac evaluation confirms that symptoms are the consequence of QT interval prolongation
- Recurrence of QTcF prolongation (confirmed by central ECG lab) after reinitiation of study treatment at a reduced dose

#### **6.7.11 Hemorrhagic Events**

Hemorrhagic events have been reported with approved drugs that inhibit VEGF pathways as well as with cabozantinib. In order to mitigate risk of severe hemorrhage, subjects should be evaluated for potential bleeding risk factors prior to initiating study treatment and monitored for bleeding events with serial complete blood counts and physical examination while on study. Risk factors for hemorrhagic events may include (but may not be limited to) the following:

- Tumor of the lung with cavitory lesions or tumor lesions which invades, encases, or abuts major blood vessels. The anatomic location and characteristics of tumor as well as the medical history must be carefully reviewed in the selection of subjects for study treatment.
- Recent or concurrent radiation
- Active peptic ulcer disease, ulcerative colitis, and other inflammatory GI diseases
- Underlying medical conditions which affect normal hemostasis (eg, deficiencies in clotting factors and/or platelet function, or thrombocytopenia)
- Concomitant medication with anticoagulants or other drugs which affect normal hemostasis
- History of clinically significant hemoptysis

Discontinue study treatment in subjects who experience a severe bleeding complication.

### **6.7.12 GI Perforation/Fistula and Non-GI Fistula Formation**

GI perforation/fistula and non-GI fistula formation have been reported with approved drugs that inhibit VEGF pathways as well as with cabozantinib. Carefully monitor for episodes of abdominal pain, especially in subjects with known risk factors for developing GI perforation/fistula or non-GI fistula, to allow for early diagnosis. Such risk factors include (but may not be limited to) the following:

GI perforation/fistula:

- Intra-abdominal tumor/metastases invading GI mucosa
- Active peptic ulcer disease, inflammatory bowel disease, ulcerative colitis, diverticulitis, cholecystitis or symptomatic cholangitis, or appendicitis
- History of abdominal fistula, GI perforation, bowel obstruction, or intra-abdominal abscess
- Prior GI surgery (particularly when associated with delayed or incomplete healing). Complete healing following abdominal surgery or resolution of intra-abdominal abscess must be confirmed prior to initiating study treatment

Additional risk factors include concurrent chronic use of steroid treatment or nonsteroidal anti-inflammatory drugs. Constipation indicative of bowel obstruction should be monitored and effectively managed.

Non-GI fistula:

- Complications from radiation therapy have been identified as a possible predisposing risk factor for non-GI fistula formation in subjects undergoing treatment with VEGF pathway inhibitors (eg, bevacizumab). Subjects are excluded from this study if there are any clinically relevant ongoing complications from prior radiation therapy (ie, radiation esophagitis or other inflammation of the viscera).

Discontinue all study treatment in subjects who have been diagnosed with GI or non-GI perforation/fistula.

#### **6.7.13 Osteonecrosis of the Jaw**

Osteonecrosis of the jaw (ONJ) has been reported with use of anti-angiogenic drugs and bisphosphonates and denosumab in cancer patients. Additional risk factors for ONJ have been identified such as use of corticosteroids, chemotherapy, local radiotherapy, poor oral hygiene, smoking, dental or orofacial surgery procedures, and cancer disease itself. Osteonecrosis has been reported in subjects treated with cabozantinib, the details of which are provided in the current version of Investigator's Brochure. As a preventive measure, invasive dental procedures should be avoided if possible. In cases where dental procedures are unavoidable, the risks and benefits of a dental procedure and the extent of the procedure as well as the risk of developing osteonecrosis of the jaw need to be considered when deciding on the duration of a temporary study treatment interruption. If clinically possible, study treatment should be held for approximately 4 weeks prior to a dental procedure and resumed after complete healing has occurred.

Subjects with any documented case of osteonecrosis should have study treatment interrupted, and appropriate clinical management should be initiated. Reinitiation of study treatment must be discussed with and approved by the Sponsor on a case-by-case basis.

## 7 CONCOMITANT MEDICATIONS AND THERAPIES

All concomitant medications used by the subject (including prescription and over-the-counter medications, transfusions, vitamins, herbal remedies, and nutritional supplements) during the period from 28 days before randomization through 30 days after the date of the decision to permanently discontinue study treatment are to be recorded in the CRF.

### 7.1.1 Allowed Therapies

Antiemetics and antidiarrheal medications are allowed prophylactically according to standard clinical practice if clinically indicated.

Granulocyte colony-stimulating factors are acceptable while the subject is enrolled in the study. However, these should not be administered prophylactically before initial treatment with study drug. Transfusions should be used in accordance with institutional guidelines.

Hormone replacement and short-term systemic steroid treatment may be utilized as indicated by standard clinical practice while the subject is enrolled in the study.

The protocol does not restrict the use of heparins at prophylactic doses. Therapeutic doses of heparins are allowed after randomization if clinically indicated for supportive treatment and the benefit outweighs the risk per the investigator's discretion (see Section 6.7.8). During treatment with anticoagulants, subjects need to be monitored on an ongoing basis for bleeding risk and signs of bleeding. Therapeutic doses of oral anticoagulants (eg, warfarin or warfarin-related agents, thrombin or FXa inhibitors, antiplatelet agents such as clopidogrel) are not allowed after randomization until study treatment is permanently discontinued.

Potential drug interactions with cabozantinib are summarized in Section 7.1.2.1 and are discussed in more detail in the Investigator's Brochure.

Subjects with active HBV should be on appropriate antiviral therapy.

